# 8.2.2 Analyses

Data will be summarized, by type of SMF reduction treatment, with descriptive statistics, and presented in listings. No formal statistical hypotheses are established for this protocol, but exploratory analyses involving inferential tests will be performed as described below.

Demographic and baseline characteristics will be summarized. Post-baseline values and change from baseline in selected outcome variables will be summarized, by type of SMF reduction treatment, with descriptive statistics, and, where appropriate, graphical presentations, and presented in listings.

# 8.2.2.1 Main Efficacy Endpoint: Submental Fat (SMF) Assessments

The following SMF assessments (Appendix 11) are planned at each visit:

- Clinician-Reported Submental Fat Rating Scale (CR-SMFRS) score
- Patient-Reported Submental Fat Rating Scale (PR-SMFRS) score
- Patient-Reported Submental Fat Impact Scale (PR-SMFIS) score
- Submental Skin Laxity Grade (SMSLG)
- Subject Self Rating Scale (SSRS)
- Patient Self-Perception of Age (SPA) scale
- Patient Global Questions

Overall and individual component summaries for each scale, where applicable, will be provided using descriptive statistics at each timepoint. Changes from baseline will be summarized descriptively for each treatment cohort at each post-baseline assessment. Exploratory analysis of covariance (ANCOVA) methods will also be used to assess change from baseline at the end-of-treatment follow-up timepoint, where treatment type and baseline score will be included in the model. The ANCOVA results will be generated in SAS using PROC MIXED. Cochran-Mantel-Haenszel (CMH) tests for association, stratified by site, will be used to assess the responses.

For CR-SMFRS and PR-SMFRS assessments, the number and percent of patients in each treatment cohort who are responders, ie, have at least a 1-grade improvement, will be presented, along with the corresponding 95% CI. Responses to the other SMF assessments will be summarized similarly.

For the SSRS, a subject is defined as a responder for the assessment if the response was positive relative to the score's neutral response option (ie, "slightly satisfied," "somewhat satisfied," or "extremely satisfied" where neutral is "neither satisfied nor dissatisfied").

An SMSLG responder at an assessment time is defined as a subject who stayed the same SMSLG score or had improvement in SMSLG score relative to baseline. This scale is different from the others in that "no change" is counted as a responder. The reason for this distinction is

that the intent is not to investigate whether ATX-101 reduces/improves skin laxity, but rather to investigate whether ATX-101 is associated with an undesirable increase in skin laxity. Accordingly, the categories are, effectively, skin laxity either "did not increase" or "did increase."

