Number of Patients	Approximately 1000 patients will be recruited from approximately 100 sites in the US and Canada.
Study Procedures	Details of the physician's practice setting will be recorded once for each site; treatment logistics will be recorded at the first treatment session for each patient.  Patients considering treatment for improvement of SM fullness due to SMF will be recruited. Eligible patients will be enrolled in the registry and data will be collected from patients who elect treatment until their SMF reduction treatment is completed or discontinued. Patients who do not initially elect treatment will be followed to determine whether or not they subsequently undergo treatment, and if not, until up to one year has elapsed since enrollment and no treatment has been elected. Physicians will treat and assess patients according to their discretion.  At enrollment, data on previous relevant SMF and facial aesthetic treatment(s) will be collected from the patients, and as necessary, their medical records, along with baseline SMF assessments and information on treatment goals. Demography (birth date, sex, race, ethnic origin), Clinical Information (height, weight, lifestyle habits), and a brief medical history (including diabetes, cardiovascular disease) will be collected, Information including treatment received for SMF reduction, treatment procedures and outcomes, follow-up assessments of SMF, and adverse events (AEs) will be recorded at subsequent clinic visits or telephone contacts (Data for Collection). Patient medical history data will be updated, as appropriate, at the first treatment visit.
Data Collection Procedures	Electronic data capture (EDC) will be used for participating sites to record clinical data, data questionnaires and assessment data via electronic case report forms (eCRFs) accessed through a secure internet portal. Data entry screens will be designed to efficiently capture the desired data elements from patient medical records (Data for Collection).
Data Elements	Physician Practice Profile At each site, the physician will complete the Physician Practice Setting Questionnaire, including the following information:  • Physician characteristics:  - Clinical history / specialty, including board certification  - Years of aesthetic practice  - Percent of practice focused on facial aesthetics  - Physician approach to discussing new treatment options  - Number and roles of physicians and other healthcare providers (HCPs) in the

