#### 3 STUDY CONDUCT

# 3.1 Design of the Study

This is a prospective, non-interventional, longitudinal, multi-center registry to be conducted in patients with SM fullness due to SMF. Each participating physician will prescribe treatments based on his or her usual clinical practice, and no restriction on the use of commercially available treatments will be imposed. As this is a non-interventional study, the patient-physician relationship will not be affected, nor will there be any influence on the therapeutic management of the patient.

Study visits, procedures, and evaluations are summarized in Data for Collection and described in detail in Sections 5 and 6.

Patients considering treatment to reduce SMF will be recruited. Eligible patients will be enrolled in the registry, and patients who elect treatment will be followed until their SMF reduction treatment is completed or discontinued. Patients who do not initially elect treatment will be followed to determine whether or not they subsequently undergo treatmentuntil up to one year has elapsed since enrollment and no treatment has been elected. Reasons for treatment discontinuation, or for the decision to not receive treatment, will be recorded. Enrolled patients will be assessed regularly by their treating physician according to usual clinical practice. Data collection is anticipated to continue for approximately 15 months. The duration of individual patient participation will vary depending on the chosen treatment method and individual requirements.

At Enrollment, relevant data on previous SMF and facial aesthetic treatments will be collected from the patients, and as necessary, from their medical records. Additionally, baseline assessments of SMF will be performed. Details of the investigator's practice setting will be recorded after site initiation, and details of treatment logistics will be recorded at the first treatment session(s) (for each treatment selected) for patients who elect treatment for SMF reduction . Information, including treatment received for SMF reduction, treatment procedures and outcomes, follow-up assessments of SMF, and adverse events (AEs) will be recorded at subsequent clinic visits or telephone contacts. Patient medical history data will be updated, as appropriate, at the first treatment session (Baseline Treatment Visit).

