#### 5.1.1 Enrollment Visit

Patients who are enrolled in the registry will have information abstracted from their medical records and undergo the baseline assessments (Section 5.3.1).

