#### **5.3** Patient and Treatment Characteristics

# **5.3.1** Demographic and Baseline Assessments

The following information will be collected at the Enrollment time point

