#### **5.3.2** Baseline Treatment Assessments

At the Baseline time point, the investigator or designee will provide information about treatment logistics within the practice, and patients will be asked to provide post-treatment data, including the following information:

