#### **End-of-Treatment SMF assessments:**

The following SMF assessments will be performed at the Final Visit (End-of-Treatment) for each SMF treatment selected:

- Clinician-Reported Submental Fat Rating Scale (CR-SMFRS) score
- Patient-Reported Submental Fat Rating Scale (PR-SMFRS) score
- Patient-Reported Submental Fat Impact Scale (PR-SMFIS) score
- Submental Skin Laxity Grade (SMSLG) score
- Subject Self Rating Scale (SSRS) score
- Self-Perception of Age (SPA) score
- Patient Global Questions (PGQ)

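### No submental fat score is clearly scheduled at the start of treatment, so change from baseline can include change that came before that treatment

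*Protocol*

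**What the plan says.** **Where the scores are taken.** Section 5.3.1 opens with "The following information will be collected at the Enrollment time point" and lists six SMF scales there under a baseline label. Section 3.1, describing what happens at Enrollment, agrees: "Additionally, baseline assessments of SMF will be performed". The synopsis lists the same six scales as Enrollment assessments.

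**A second meaning of baseline.** The Baseline Treatment Visit (Section 5.1.2) is the first session of each treatment selected. For that time point Section 5.3.2 says that "the investigator or designee will provide information about treatment logistics within the practice, and patients will be asked to provide post-treatment data". It then lists logistics, pain, procedures and adverse events, and no SMF scale. In the Data for Collection table, the Baseline column shows no mark against the SMF scales.

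**Statements that point the other way.** Section 8.2.2.1 says: "The following SMF assessments (Appendix 11) are planned at each visit". Section 5.1.2 has treatment outcomes recorded at the first session, but refers for the content to Section 5.3.2, which contains none. Appendix 11.2 speaks of scoring the clinician scale at both screening and baseline.

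**After treatment starts.** Section 5.3.3 repeats the scales at Follow-up for each treatment, and Section 5.3.4 does the same at the end: "The following SMF assessments will be performed at the Final Visit (End-of-Treatment) for each SMF treatment selected". Section 8.2.2.1 then analyses them: "Changes from baseline will be summarized descriptively for each treatment cohort at each post-baseline assessment". It adds responder rates (improvement of at least one grade) and an exploratory ANCOVA with treatment type and baseline score.

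**Late election.** Patients who do not elect treatment at first are followed "until up to one year has elapsed since enrollment and no treatment has been elected" (synopsis; Section 3.1 is similar).

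**The concern.** Change from baseline describes a treatment only if the baseline belongs to the start of that treatment. Under the detailed schedule this fails for two groups.

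- **Late electors.** Their only pre-treatment score is from Enrollment, possibly many months earlier. Any change in between is counted as treatment effect.
- **Patients with more than one treatment.** Post-treatment scores are repeated for each treatment, but no treatment-specific baseline is scheduled. If the Enrollment score serves for the later treatment, that treatment also carries the effect of the earlier one.

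The error need not flatter the later treatment. For the skin laxity grade, where a responder is a patient whose laxity did not increase, laxity caused by one treatment could be charged to the next.

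At stake are the cohort summaries of what the protocol calls its main efficacy endpoint. A statistical analysis plan can choose among scores that were collected, but it cannot recover a score that was never taken.

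**Working it through.** **1. The passages side by side**

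| Time point | SMF scales in the detailed lists and table | SMF scales per Section 8.2.2.1 |
|---|---|---|
| Enrollment | Yes | Yes |
| Baseline Treatment Visit (each treatment) | None | Yes, if every visit is meant |
| Follow-up (each treatment) | Yes, without self-perception of age | Yes |
| End-of-Treatment (each treatment) | Yes, plus Patient Global Questions | Yes |

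The table's cells run together in the text at hand, but the Baseline cell of the SMF block is empty and the written lists in Section 5.3.2 and the synopsis agree with it. The statement in Section 8.2.2.1 cannot be literally true: it includes self-perception of age, which is not in the Follow-up list, and the Patient Global Questions, which are listed only at End-of-Treatment. It therefore does not override the detailed schedule. A site working from the lists would collect no SMF score at the first session.

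**2. Age of the baseline for late electors**

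Inputs: election up to 12 months after Enrollment (synopsis) and data collection of about 15 months (Section 3.1). The baseline can be 0 to about 12 months old at first treatment. The extreme requires enrollment by about month 15 − 12 = 3, and earlier still to leave time for treatment. Medical history is updated at the first session, but the outcome is not re-rated. Weight is scheduled at Enrollment and at End-of-Treatment, so its overall change is known but cannot be split into before and after the start of treatment.

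**3. The plan's own precision figure**

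Section 8.1, Table 1 gives 61.7 to 73.3 for a 67.5% response rate at N = 250. The formula p ± 1.96 × √(p(1 − p)/N) gives 67.5 ± 5.8, or 61.69 to 73.31. The table reproduces and is not in dispute. The 5.8 points serve only as a yardstick below.

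**4. Carry-over, as an illustration**

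Let r be the response rate to an earlier treatment, q the later treatment's own response rate, and f the share of the later cohort treated earlier. Assume independent responses, no relapse, and the Enrollment score as baseline. A previously treated patient then counts as a responder with probability 1 − (1 − r)(1 − q). The excess over q is r(1 − q), so the cohort bias is f × r × (1 − q).

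Only 67.5% comes from the protocol, and it is the Phase 3 rate for ATX-101, not for an arbitrary first treatment. All other inputs are assumptions.

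| r | q | f | Bias (points) |
|---|---|---|---|
| 67.5% | 40% | 10% | 0.10 × 0.675 × 0.60 = 4.1 |
| 67.5% | 40% | 20% | 0.20 × 0.675 × 0.60 = 8.1 |
| 67.5% | 40% | 30% | 0.30 × 0.675 × 0.60 = 12.2 |
| 20% | 40% | 20% | 0.20 × 0.20 × 0.60 = 2.4 |
| 67.5% | 0% | 25% | 0.25 × 0.675 × 1.00 = 16.9 |

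If a score from after the earlier treatment and before the later one is used as baseline, the carry-over is removed for the patients who have such a score. The range is thus 0 to about 17 points, on either side of the 5.8-point half-width.

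**The case against.** **Reuse of the Enrollment score is not stated.** A reader might infer a rule that every treatment is measured from Enrollment. No passage says so. Which record serves as baseline for a second treatment is ordinary content for the analysis plan, to which the protocol refers. For treatments in sequence a later score should often exist, because End-of-Treatment scales are due for each treatment within 3 months of its last session. This stands, and the carry-over concern is conditional on it. It does not cover overlapping or combined treatments. Nor does it guarantee a usable score, since Section 5.1.4 also allows the Final Visit after all treatments are complete.

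**The ANCOVA.** A reader might also infer that it enters two records of one patient as independent. The protocol defines neither cohort membership for such patients nor the number of records per patient, and the procedure it names can model within-patient correlation. That inference is not supported.

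**The numbers.** The shares and response rates are assumed. Patients who seek a second treatment may be mostly non-responders to the first, and with r = 20% the bias at f = 20% falls to 2.4 points. The 8.1-point figure does not demonstrate material bias. A year-old baseline is likewise the extreme case, not the typical one.

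**The setting.** The registry is non-interventional, has no formal hypotheses and uses inferential tests only for exploration. This lowers the severity. It does not supply the missing score.

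**Conclusion.** The concern holds in a limited form and should be fixed.

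- **Firm:** the protocol contradicts itself on whether SMF scales are scored at the first session, and its detailed schedule omits them. If that schedule is followed, patients treated well after Enrollment have no score at the start of treatment, and later analysis cannot restore it.
- **Conditional:** a second, overlapping or combined treatment may be credited with an earlier one's effect. This depends on whether a prior End-of-Treatment score is available and used as baseline.
- **Size:** unknown. The protocol gives neither the share of late electors nor that of multi-treatment patients. The 0 to 17 points above illustrate carry-over only, under assumed inputs, independence and no relapse. Drift before treatment in late electors is not quantified at all.

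The consequence is possible bias in descriptive cohort summaries and exploratory contrasts, not a failed hypothesis test.

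**What to change.** 1. Reconcile the Data for Collection table and Sections 5.1.2, 5.3.2 and 8.2.2.1. Schedule the SMF scales before the first session of each treatment whenever that session is not on the Enrollment day.
2. Define baseline for each treatment as the last SMF score on or before its first session. Use that definition for the cohort changes from baseline, the responder rates and the ANCOVA.

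The cost is one more column of ratings, a few minutes at a visit that already takes place, plus the wording of the definition. The change has to be made while patients are still being enrolled and treated, because missed scores cannot be collected afterwards.

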Statistical Methods	A formal statistical analysis plan (SAP) that will provide details of all analyses and presentation of registry data will be approved prior to data analysis.
	Descriptive statistics will comprise the number of observations (n), mean, standard deviation (SD), median, minimum, and maximum for continuous variables; and n and percent for categorical variables, with the number of patients who do not have missing values as the denominator.
	No imputation for missing data will be performed. Analyses will be conducted using observed cases.
Sample Size	Up to 1,000 patients are anticipated. The number and size of analysis groups will be determined by the treatments selected by the patients in this sample; therefore, group sizes may not be identical. In general, if the sample size in a treatment cohort is at least 250, this study is well-powered to observe an improvement of at least one grade in the CR-SMFRS (Section 8.1)
Analysis Populations	Analyses will be based upon all patients who were enrolled and have at least one post-baseline visit. Additional subgroups also may be examined, as deemed appropriate (eg, sex, initial assessment scores, prior treatments received).
Practice, Patient, and Treatment Data	Data will be summarized, by type of SMF reduction treatment, with descriptive statistics, and presented in listings.
Outcome Data	SMF Assessments
	Results for SMF assessments will be summarized with descriptive statistics at each time point. Changes from baseline will be summarized descriptively for each

CONFIDENTIAL

gistry Study Protocol

treatment cohort at each post-baseline assessment. Exploratory analysis of covariance (ANCOVA) methods will also be used to assess change from baseline at the end-of-treatment follow-up timepoint, where treatment type and baseline score will be included in the model. The ANCOVA results will be generated in SAS using PROC MIXED. Cochran-Mantel-Haenszel (CMH) tests for association, stratified by site, will be used to assess categorical responses. The qualification for a "responder" for each SMF assessment will be further defined in the SAP. For the CR-SMFRS and PR-SMFRS assessments, the number and percent of patients in each treatment cohort who have at least a 1-grade improvement will be presented, along with the corresponding 95% confidence interval (CI). Responses to the other SMF assessments will be summarized similarly.

Protocol ATX-101-15-40M

Amendment 2: 20 Oct 2015

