#### **DATA FOR COLLECTION**

	Site Screening	Enrollment (all patients)	Baseline (treated patients)	Follow-up (treated patients)	End-of-Study (untreated patients)	End-of- Treatment (treated patients)
Physician Practice Setting Questionnaire a	X					
Patient Population Informed consent / medical records release /brief medical history Demography & Clinical Information Patient Treatment History Patient Treatment Goals Questionnaire Physician Treatment Goals Questionnaire		X X f X X			X f	X f
Treatment Logistics: Treatment Logistics Questionnaire Pain Numeric Rating Scale Treatment Procedures Questionnaire			X b X e X c	Xe		X e
Adverse Events: Adverse Event Log			$X^{b}$	$X^{b}$		X b
Treatment Outcomes & Follow-up:  SMF assessments:  Clinician-Reported Submental Fat Rating Scale (CR-SMFRS) score Patient-Reported Submental Fat Rating Scale (PR-SMFRS) score Patient-Reported Submental Fat Impact Scale (PR-SMFIS) score Submental Skin Laxity Grade (SMSLG) Subject Self Rating Scale (SSRS) Patient Self-Perception of Age (SPA) scale Patient Global Questions (PGQ) Patient End-of-Treatment Questionnaire Physician End-of-Study Questionnaire Patient End-of-Study Questionnaire		X X X X X		$egin{array}{c} X^b \ X^b \ X^b \ X^b \ X^b \ \end{array}$	X d	X b

- a: Physician Practice Setting Questionnaire is to be completed once for each site at the start of the study (following site initiation).
- b: To be completed only for patients who elect a SMF reduction treatment (treated patients). (Applicable time points: Baseline, Follow-up, End-of-Treatment).
- c: To be completed only for patients treated with ATX-101. (Applicable data point(s): Treatment Procedures Questionnaire).
- d: To be completed only for untreated patients. (Applicable data point: Patient End-of-Study Questionnaire)
- e: To be completed only for patients who elect a SMF reduction treatment (treated patients) at the following applicable time points: Baseline, Follow-up, and End-of-Treatment. Patients treated with ATX-101 will be asked to provide pain scores at each ATX-101 treatment visit.
- f: Demography (birth date, sex, race, ethnic origin) & Clinical Information (height, weight, lifestyle habits) to be collected at Enrollment; Clinical Information (height, weight) to be collected at End-of-Treatment / End-of-Study for all patients.

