#### 5.1.4 Final Visit

The patient's Final Visit will take place either at the last scheduled follow-up visit after completion of all SMF reduction treatment(s), within 3 months of the last treatment session (for each treatment selected), when a patient elects to discontinue treatment, or prior to study closure (treated patients). Information on AE/SAEs, treatment outcomes, and End-of Study assessments will be recorded (section 5.3.4). For patients who do not elect treatment for SMF reduction (untreated patients), the reason for not selecting treatment will be captured at this time point.

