# 9.8.2 Confounding Bias

An objective of this study is to better understand characteristics of practices, providers, and patients that influence the selection and outcomes of aesthetic treatments. The intent is to collect sufficient data to evaluate these predictors and adjust for them, as applicable, in the analyses. The collection of retrospective and baseline information will permit outcomes to be compared in light of differences prior to treatment selection.

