#### 9.8.3 Effect Modification

Characteristics such as obesity, age, skin laxity, etc. will be associated not only with treatment routing (selection bias) but also with outcomes. Again, this information will be used as appropriate in evaluating outcome data.

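### The exploratory between-treatment ANCOVA and CMH tests in Section 8.2.2.1 do not make the adjustment for obesity, age and skin laxity that Sections 9.8.2 and 9.8.3 announce

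*Protocol*

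**What the plan says.** Treatment is not randomised. Section 3.1 of the protocol states: "Each participating physician will prescribe treatments based on his or her usual clinical practice".

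Section 8.2.2.1 plans an exploratory ANCOVA of change from baseline at the end-of-treatment time point, "where treatment type and baseline score will be included in the model". The synopsis, under Outcome Data, repeats this: "treatment type and baseline score will be included in the model. The ANCOVA results will be generated in SAS using PROC MIXED". Responder outcomes are assessed in both places by CMH tests whose only stratification factor is site.

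Two later sections deal with comparability. Section 9.8.2, on confounding, refers to characteristics of practices, providers and patients that influence treatment selection and outcome, and says: "The intent is to collect sufficient data to evaluate these predictors and adjust for them, as applicable, in the analyses". Section 9.8.3 says: "Characteristics such as obesity, age, skin laxity, etc. will be associated not only with treatment routing (selection bias) but also with outcomes". It adds that "this information will be used as appropriate in evaluating outcome data". Neither section names a model, a covariate list or a method.

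The data for such an adjustment are planned. The notes to the Data for Collection table say: "Demography (birth date, sex, race, ethnic origin) & Clinical Information (height, weight, lifestyle habits) to be collected at Enrollment". Section 5.3.1 lists the SMSLG among the baseline assessments and also records facial aesthetic treatment over the preceding 24 months.

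**The concern.** A variable related both to which treatment a patient receives and to how that patient fares is a confounder. Section 9.8.3 describes exactly this for obesity, age and skin laxity, although its heading speaks of effect modification. The comparative analyses that Section 8 names contain none of the three. The one partial exception is the model for SMSLG itself, where the baseline score already is laxity. The CMH test does not account for baseline severity either.

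An analysis that follows Section 8.2.2.1 to the letter would therefore give a between-treatment contrast that combines any treatment effect with differences in case mix that the registry has measured. Section 9.9 allows results to be presented at conferences from time to time, where a p-value from such a model can be read as comparative effectiveness even though the analysis is exploratory.

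**Working it through.** **1. The plan's own figures.** The protocol gives no power or precision for the ANCOVA. Its figures in Section 8.1 are intervals around single proportions, p ± 1.96·√(p(1−p)/N). For p = 0.675 and N = 250 the half-width is 1.96·√(0.675·0.325/250) = 0.058, giving 61.7 to 73.3 as in Table 1. All 3 intervals in Table 1 and all 9 in Table 2 reproduce to 0.1 point. None of them depends on the ANCOVA, so no stated figure is wrong on this point.

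**2. The text set side by side.**

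| Characteristic | Section 9.8.3: related to treatment choice and outcome | Available at Enrollment | In the ANCOVA as named | In the CMH as named |
|---|---|---|---|---|
| Obesity | yes | yes (height, weight) | no | no |
| Age | yes | yes (birth date) | no | no |
| Skin laxity | yes | yes (SMSLG) | only when SMSLG is the outcome | no |
| Baseline score of the outcome | not named | yes, for the scales scored at Enrollment | yes | no |
| Site | not named | yes | no | yes |

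**3. One omitted covariate.** The protocol gives no confounder strengths, so every input here is an assumption: SD of CR-SMFRS change 0.8 grade; cohorts of 250 and 100; an omitted covariate with partial correlation r to change; and a difference of d SD between cohorts on that covariate.

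- Bias = d · r · 0.8 grade.
- SE = 0.8·√(1/250 + 1/100) = 0.0947 grade.
- Rejection with no true difference = P(|Z + bias/SE| > 1.96).

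| d | r | Bias (grade) | Bias/SE | Rejection at nominal 5% |
|---|---|---|---|---|
| 0.25 | 0.1 | 0.02 | 0.21 | 5.5% |
| 0.5 | 0.2 | 0.08 | 0.85 | 14% |
| 1.0 | 0.3 | 0.24 | 2.53 | 72% |

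**4. Three omitted covariates together.** A simulation with zero true treatment effect used 1000 replicates per setting and standardised age, BMI and laxity. The assumed log-odds of treatment choice were 0.2 to 0.6 per SD, and the assumed effect on outcome was 0.1 to 0.2 residual SD per SD. All three covariates act in the same direction.

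| Setting | Two-term bias (residual SD) | Two-term rejection | Rejection with the three covariates added |
|---|---|---|---|
| N = 500, split 1:1 | 0.06 to 0.29 | 9% to 87% | 4.0% to 5.8% |
| N = 1000, split about 75:25 | 0.06 to 0.30 | 12% to 98% | 4.3% to 6.9% |

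With the covariates added, the mean bias is within 0.004 SD of zero. When the covariates are unrelated to treatment choice, the two-term model is unbiased and rejects 4% to 6% of the time. The problem therefore depends on the link that Section 9.8.3 asserts. Covariates acting in opposite directions would partly cancel, so these ranges show what is possible and are not a forecast.

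**The case against.** The strongest reply is that the protocol leaves adjustment open. Section 8.2.2.1 says that two terms go into the model, not that nothing else may. Sections 9.8.2 and 9.8.3 can be read alongside it, and Section 8 assigns the details of all analyses to an SAP that is not at hand. This stands in part. A reader might infer that the model is closed to further terms, or that Section 8 flatly contradicts Section 9.8.2; the wording supports neither. But the model terms are stated twice without any deferral. Elsewhere the protocol says when a specific choice is left to the SAP, for example additional groups (Section 8.2.1) and attrition (Section 9.8.4). An SAP that copied the named model would not deliver the announced adjustment.

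Second, the objective is descriptive, Section 8.1 sets no hypotheses, and Section 8.2.2 calls the inferential tests exploratory. This stands and limits the consequence. It does not make the contrast interpretable.

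Third, Section 4.2 excludes severe laxity, which narrows one of the three confounders. That reduces its possible influence but does not remove it.

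A reader might also count assessment timing as an omitted confounder, because Section 5.1.4 lets the Final Visit fall anywhere up to 3 months after the last session, at discontinuation, or before study closure. The documents do not support this. Nothing says that timing differs by treatment type. The interval arises after treatment choice, so adjusting for it could distort the contrast. Session-by-session data are described only for ATX-101 (Section 5.3.2), and no last-session date is listed for other treatments.

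**Conclusion.** The point holds in limited form. The exploratory between-treatment ANCOVA and the CMH tests, as named in Section 8.2.2.1 and the synopsis, do not carry out the adjustment that Sections 9.8.2 and 9.8.3 announce. As written, they give contrasts confounded by characteristics that the registry measures at Enrollment.

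The size cannot be stated from the documents. The illustrative bias is 0.02 to 0.24 grade for one covariate and 0.06 to 0.30 residual SD for three. The lowest case is close to nominal error, and the 72% figure needs a full 1 SD imbalance between cohorts.

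Three further inferences go beyond the text. Section 9.8.3 speaks of association and does not say that these variables drive treatment choice or outcome. The ANCOVA is not the only planned comparison, since the CMH tests are another. The descriptive within-cohort summaries, responder rates with their intervals, and safety tables do not depend on this model and are not called into question. The change is worth making but is not critical to the registry's main purpose.

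**What to change.** In Section 8.2.2.1 and the synopsis:

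- Add to the ANCOVA the Enrollment covariates age, sex, BMI, baseline SMSLG (already the baseline score when SMSLG is the outcome) and facial aesthetic treatment in the preceding 24 months.
- Keep the two-term model as a reference, labelled as not adjusted for these confounders.
- Beside the CMH test, fit a logistic model for responders with treatment type, the baseline score and the same covariates.
- Leave time from last session to assessment out of the main model. At most, use it in a sensitivity analysis where it is available.

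The cost is a wording change in the protocol, matching text in the SAP, and a few model terms drawn from data already planned. The analysis gives up a few degrees of freedom and, because Section 8 rules out imputation, any patient with a missing covariate. Unmeasured confounding remains, so the adjusted contrast still needs that caveat.
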